9. RISK ANALYSIS

The decision to repair an aortic aneurysm is generally based on the risk of rupture, the risk of complications of surgery, and patient preference. There are currently two methods used to repair aortic aneurysms. The conventional method is an open surgical repair, with the implantation of a synthetic graft to replace the diseased aneurysmal vessel through a large abdominal incision. More recent technological developments have resulted in an alternative, minimally invasive, endovascular aneurysm repair, in which a prosthesis is placed within the aorta through a small incision in the groin. Blood can then flow through the implanted device and is excluded from the aneurysmal portion of the aorta.

The disadvantages of open surgical repair are: general anesthesia is required, it is a major abdominal surgery (large incision), has a significant surgical complication rate, and typically requires a long hospital stay and recovery. EVAR/EVAS enables local or regional anesthesia to be used, uses a minimally invasive groin incision for catheter-based access, and has been reported in multiple studies to offer a lower perioperative complication rate, reduced blood loss and procedure times, and shorter hospital stay. In contrast to open repair, EVAR/EVAS is a relatively new treatment, long term results have not been fully established, and life-long surveillance is recommended to verify implant integrity and patency and continued aneurysm exclusion. Multiple device systems are CE Marked and marketed in the European Community for endovascular abdominal aortic aneurysm repair. All of these devices require the introduction of catheter-based treatment devices varying in outer diameter profile. Standard vascular exposure is indicated for access. Prospective clinical study results support the safety and effectiveness of these devices through early follow-up (to 30 days) and for some in late follow-up to one year and beyond to up to five years.

As with any procedure there are risks of serious complications, such as death. The inclusion and exclusion criteria for this population have been carefully established to limit the risk of mortality and morbidity in this population. The overall risk will be evaluated on an individual basis and discussed with each patient. All of the potential adverse events outlined previously could cause prolonged illness, permanent impairment of daily function or, in rare cases, death. Possible treatments could include, but are not limited to, emergency cardiac or vascular surgery.

Eligibility criteria that exclude subjects who are at higher risk for experiencing an anticipated adverse event have been selected to reduce the potential risks to subjects who participate in this study. In addition, the assessment of patient computed tomography angiography imaging by an experienced Core Laboratory is also intended to reduce the potential risks to subjects who participate in this study.

Pre-procedural high resolution, contrast-enhanced CT scanning and intraprocedural arteriography will be used to identify and target the aortic anatomy to facilitate the proper introduction, delivery, and deployment of the endovascular repair devices. Physician experience, rigorous application of a common protocol, and careful performance of the procedure with close monitoring of the patient after the procedure will also help to minimize risks.

The alternative to endovascular repair of AAA is open surgical repair.

10. STATISTICAL PROCEDURES

10.1 ANALYSIS POPULATIONS

All primary analyses will be conducted on an intention to treat (ITT) basis. Whereas ITT is a concept intended to be applied to randomized trials, its use in this analysis will imply that subjects will be analyzed based on the attempt to implant trial devices during the procedure. Subjects who complete the trial through 12 month follow-up, or have expired prior to 12 month follow-up, will comprise the Completed Cases (CC) population. Additional analyses will be conducted in the CC population. Completed Cases subjects who have an implanted device and are alive upon exit from the procedure room will be considered per protocol (PP) population. All roll-in subjects treated will be evaluated as a separate feasibility group.

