- Device performance (aneurysm sac diameter change from the first post-operative CT scan; device migration; incidence of endoleak) at 30 days, 6 months, and annually to 5 years;
- Renal function as assessed by estimated glomerular filtration rate (eGFR) pre-discharge and at 30 days, 6 months, and annually to 5 years;
- Device Patency and Integrity at 30 days, 6 months, and annually to 5 years;
- Luminal Thrombus Requiring Intervention at 30 days, 6 months, and annually to 5 years
- Secondary endovascular procedure or open surgery within 30 days, at 6 months, and annually to 5 years for resolution of endoleak (Type I or III), device occlusion, migration, aneurysm sac expansion and/or a device defect.

Schedule of Tests: Pre-procedural high resolution, contrast-enhanced CT scan evaluation to determine anatomical eligibility for enrollment will be performed within three months of the study procedure. Following EC/IRB approval of the study and the written informed consent form, patients will be screened for eligibility. Following informed consent, a physical exam and laboratory testing will be performed prior to the procedure. Subjects will be followed procedurally and to hospital discharge, and will then be followed at intervals: 30 days; 6 months; 1 year; and annually to 5 years.

Statistical Considerations:

Study Population: The Intent To Treat (ITT) population in this study consists of all subjects who are enrolled with an attempt to implant the Study Device. All roll-in subjects will be evaluated as a separate group. The subject is considered enrolled when the study device enters the access vessel.

The Per Protocol (PP) population in this study consists of all ITT subjects that have a device implanted and are alive when exiting the procedural room.

The Completed Cases (CC) population consists of all PP subjects that have completed 12 month follow-up visit.

Study Success, Safety: The primary safety analysis is **Major Adverse Events (MAE)**, as previously defined. The primary endpoint is to show that the percentage of subjects with an MAE is statistically superior to that in the Society for Vascular Surgery (SVS) open surgical control group at 30 days (56%). The hypothesis test

will be evaluated by the exact test as a one-tailed test, using significance level $\alpha=0.025$. Multivariable analyses will be used to assess predictors of success.

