8.5.4. Subject Enrollment

Enrollment in the study only occurs upon advancement of the study device into the subject's vasculature. Therefore, the date of study enrollment is the date of the Nellix System implant, as documented in the Visit Date field in the Index Procedure eCRF. If the device does not contact the patient, the patient will be considered as screen failure and the assigned study number will not be given to another patient. If, during the index procedure, the device is introduced but is not implanted and/or there is conversion to open surgery, the patient will be followed until the 30 day follow-up.

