The primary imputation will be done 10 times with 10 different seeds to initiate the random selection and the combined P-value for the 10 imputations will be obtained by a method described in Rubin (1987) and in the SAS manual for PROC MIANALYZE. The seeds to be used for the 10 imputations are selected from a pseudo-random number table in Steele and Torrie (1960) and are 70303, 18191, 62404, 26558, 92804, 15415, 02865, 52449, 78509, and 43896.*

With regard to imputation for the primary safety endpoint, that endpoint is obtained so close to the procedure that there will be very little missing data. If any of the test subjects are lost to follow-up prior to 30 days, that patient will be assigned an MAE for primary analysis purposes.

In addition to the above missing data analyses, Tipping Point analyses will also be performed. For each imputed data set, one MAE will be added and the exact binomial test will be done. The number of steps required to achieve non-significance of the MAE endpoint will be reported for each imputation. The supportive tipping point analysis will be repeated for the completed cases and will be done in the same way by adding one MAE and doing an exact binomial test of the result. The number of steps required to achieve non-significance will be reported for this analysis as well.

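### The synopsis and section 10.1 nest the Completed Cases and Per Protocol populations in opposite orders, and they disagree on whether deaths before 12 months belong in Completed Cases

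*Combined protocol and SAP*

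**What the plan says.** The synopsis (section 3, Statistical Considerations, Study Population) starts from ITT. PP "consists of all ITT subjects that have a device implanted and are alive when exiting the procedural room". CC is then cut from PP: "The Completed Cases (CC) population consists of all PP subjects that have completed 12 month follow-up visit". The order is CC within PP within ITT.

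Section 10.1 starts from CC: "Subjects who complete the trial through 12 month follow-up, or have expired prior to 12 month follow-up, will comprise the Completed Cases (CC) population". PP is then cut from CC: "Completed Cases subjects who have an implanted device and are alive upon exit from the procedure room will be considered per protocol (PP) population". The order is PP within CC.

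On use, section 10.1 states "All primary analyses will be conducted on an intention to treat (ITT) basis" and then "Additional analyses will be conducted in the CC population". Section 10.2 adds, for the 30-day MAE endpoint, "The supportive tipping point analysis will be repeated for the completed cases". Sections 10.1 to 10.9 assign no analysis to PP. Section 8.5.4 says that if the device is introduced but not implanted, or there is conversion to open surgery during the index procedure, "the patient will be followed until the 30 day follow-up".

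**The concern.** Two current passages give the same labels to different sets of subjects, and nothing says which governs. A programmer working from the synopsis and one working from 10.1 would produce different completed-cases tables from the same data, and the choice could be made after the results are known.

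The difference in CC depends on outcome. A subject who leaves the procedure room with the device and dies at month 3 is in CC under 10.1 and out of it under the synopsis, because that subject died. All-cause death is a component of the MAE composite (section 6.1). Under the synopsis, then, the completed-cases repeat of the MAE tipping point omits every subject who died within 30 days.

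There is a linked gap. Under 10.1 the deaths enter the CC denominator, but the Treatment Success definition (synopsis, 6.2 and 10.7.2) does not list death. The plan does not say whether these subjects count as successes or failures.

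**Working it through.** The documents give no PP or CC counts, so there is no stated figure to reproduce. The first step compares the definitions as sets; the second shows a possible size.

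**Step 1. Membership by type of subject**

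| Subject | Synopsis PP | 10.1 PP | Synopsis CC | 10.1 CC |
|---|---|---|---|---|
| Implanted, completes 12 months | in | in | in | in |
| Implanted, leaves room alive, dies before 12-month follow-up | in | in | **out** | **in** |
| Dies in the procedure room | out | out | **out** | **in** |
| Not implanted, dies before 12 months | out | out | **out** | **in** |
| Not implanted, survives, exits at 30 days (8.5.4) | out | out | out | out |
| Implanted survivor, lost before 12 months | **in** | **out** | out | out |

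CC differs on deaths. PP differs only on implanted survivors without 12-month completion; on deaths the two PP definitions agree.

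**Step 2. Illustrative counts (assumed)**

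Take 150 enrolled, with 3 not implanted and exiting alive at 30 days, 5 deaths after leaving the room and before 12 months, and 15 lost. The 15 are 10% of 150, in line with the missing-data rate expected in 10.2.

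- Completers: 150 − 3 − 5 − 15 = 127.
- Synopsis: PP = 150 − 3 = 147; CC = 127.
- Section 10.1: CC = 127 + 5 = 132; PP = 132, since all of these were implanted and left the room alive.

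**Step 3. Effectiveness in CC**

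This assumes that the unspecified additional analyses include the effectiveness test. Goal 0.80, one-sided alpha 0.05 (10.7.1), p = P(X ≥ x | n, 0.80). Assume 113 successes among the 127 completers.

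- Synopsis CC: 113/127 = 89.0%, p = 0.005.
- 10.1 CC, deaths as failures: 113/132 = 85.6%, p = 0.0625.
- 10.1 CC, deaths as successes: (113 + 5)/132 = 118/132 = 89.4%, p = 0.003.

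With deaths as failures, the choice of page moves the result across 0.05.

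**Step 4. MAE tipping point in CC**

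Goal 0.56, one-sided alpha 0.025 (10.6.1); planned MAE rate 16.6% (10.6.2). The test is significant while P(X ≤ x | n, 0.56) < 0.025.

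- 10.1 CC, n = 132: expected MAEs 0.166 × 132 ≈ 22. The largest significant count is 62, so 63 − 22 = 41 added MAEs reach non-significance.
- Synopsis CC, n = 127, if all 5 deaths fell within 30 days: 22 − 5 = 17 MAEs remain. The largest significant count is 59, so 60 − 17 = 43 added MAEs are needed.
- Synopsis CC, if none of the 5 who died had a 30-day MAE: 22 MAEs remain, and 60 − 22 = 38 are needed.

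The count is 41 under 10.1 and 38 to 43 under the synopsis.

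**The case against.** The strongest reply is that no decision in the trial depends on this. Every primary analysis is ITT, no analysis is assigned to PP, the sample size is unaffected, and the safety margin is so wide that a completed-cases tipping point near 40 added events says the same thing under either definition. All of that stands, and it limits the point to supportive analyses. It does not remove the point, because 10.1 plans analyses in CC and 10.2 repeats one there by name.

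A reader might also infer more than the text supports:

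- *That the two places treat deaths oppositely throughout.* They do so only for CC. Both PP definitions drop in-room deaths and keep later ones.
- *That PP rests only on implantation and survival in both places.* Section 10.1 also requires 12-month completion or death.
- *That the synopsis CC strips out the safety failures as a class.* Section 6.1 lists seven non-fatal components besides death, and survivors with those events who complete 12 months remain. Only subjects who died are lost.
- *That the 147 versus 132 gap in PP distorts a planned result.* No planned result uses PP.
- *That PP must be redefined by eligibility deviations.* Both texts agree on implanted and alive at exit. Changing that is a design preference, and section 8.7 has no class of major eligibility deviation to draw on.

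**Conclusion.** The contradiction is certain: it rests on set definitions in current text, and no reading satisfies both. The plan should be corrected, but the consequence is confined to supportive analyses.

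For effectiveness in CC the conflict can matter: p = 0.005 against p = 0.0625 in the illustration. That rests on assumed counts (127 completers, 113 successes, 5 deaths), on the effectiveness test being among the additional CC analyses, and on deaths being scored as failures, which the plan does not state. If deaths are scored as successes, the two definitions agree on significance. For the 30-day MAE tipping point the effect is small, and the safety conclusion does not change at the planned rate. The objection to the synopsis version there is one of principle: it excludes subjects because of an event that the endpoint counts.

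**What to change.** 1. Replace the synopsis definition of CC with the one in 10.1: subjects who complete 12-month follow-up or die before it, with no restriction to PP subjects.
2. Choose one definition of PP and print it in both places, saying whether an implanted survivor lost before 12 months is in or out.
3. State how a death before 12 months is scored for Treatment Success in CC, since the endpoint does not list death. Without this, matching definitions would still leave the CC effectiveness result open.

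All three should be settled before database lock. The cost is wording in the synopsis and 10.1 and one scoring rule; no new data are needed. The downside is that deaths enter the supportive CC figures, which may look slightly less favourable.

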10.2 PATIENT ACCOUNTABILITY AND MISSING DATA

The proportion of subjects with documented follow-up at each interval will be presented descriptively. The number of diagnostic, laboratory, and clinical evaluations will be tabulated by follow-up interval. Also, a listing of patients who initially consent but do not undergo a procedure due to withdrawal of consent prior to procedure will be given. However, these subjects will not be included in any analysis.

Information on missing or withdrawn subjects will be tabulated presenting the number and proportion of subjects eligible for and compliant with each follow-up examination. Subjects who withdraw from the trial will be tabulated with the reasons for the withdrawal. Additional sensitivity analyses will be performed as described below.

The evaluation of subjects with missing data presents a special concern in ITT analyses. All clinical studies analyze the results based on the completed cases (i.e., those who complete the trial). Because missing subjects do not have final data, they present a problem for ITT analyses. The statistical community recommends that multiple sensitivity analyses be conducted to determine the robustness of the result in subjects who complete the study.^{*,†‡§} The intention of these analyses is to demonstrate that the results obtained from the evaluable subjects are not biased.

As a result, sensitivity analyses using multiple imputations will be conducted to evaluate the robustness of the study result accounting for missing observations. The primary effectiveness endpoint analyses will be recalculated using an unbiased imputation of the determination of success or failure. It is expected that the number of subjects with missing effectiveness data at one year will be approximately 10% of study enrollment. The first method of imputation will be to assign values using a simple random sample from the subjects with outcomes at one year. This system is denoted the “Hot Deck by Simple Random Sampling with Replacement”.^{**} The number of subjects to impute is small and trying to

^{*}Pocock S. (1983). Clinical Trials (A Practical Approach). John Wiley and Sons, Chichester.

[‡]Guidance for Industry: E9 Statistical Principles for Clinical Trials. U. S. Department of Health and Human Services, Food and Drug Administration, Center for Drug Evaluation and Research and Center for Biologics Evaluation and Research. International Committee on Harmonization, September 1998.

[§]Rubin D. Multiple Imputation for Nonresponse in Surveys. 1987: John Wiley and Sons, New York.

^{**}Little R and Rubin D. Statistical Analysis with Missing Data. 2002. John Wiley and Sons, New York.

Confidential. This document and the information contained herein may not be reproduced, used or disclosed without written permission from Endologix, Inc.

provide a more sophisticated imputation method would require modeling missingness with only approximately 10% of enrolling subjects or less with missing data. Additional sensitivity analyses will be done by using other imputation methods; Last Observation Carried Forward (LOCF); subjects lost to follow-up considered an endpoint failure; impute the missing result as having succeeded the endpoint; and impute the missing value by a generating a random number and comparing it to the value of the performance goal for effectiveness.

A comparison of baseline characteristics of the subjects with missing data and those without missing data will be done to determine if there is evidence that the data are not missing at random (it is not possible to determine that data are missing at random). If the missing at random assumption is clearly violated by these comparisons, it is usually possible to find a sub-group that are not missing at random who have to be imputed differently, such as assigning the worst score to subjects in the sub-group. For example, the proportion of subjects missing an outcome may be much greater at a given study site which may also have a higher rate of failure. Those subjects from that site may be assigned a failure and the baseline comparisons of the remaining subjects will be rechecked to see if the imbalances are resolved. If this resolves the missing at random difficulty, the sub groups will be given special scores and the remaining subjects will be imputed as described above. The resolution of the imbalance will be retested by the same methods with the subjects identified above removed.

The primary imputation will be done 10 times with 10 different seeds to initiate the random selection and the combined P-value for the 10 imputations will be obtained by a method described in Rubin (1987) and in the SAS manual for PROC MIANALYZE. The seeds to be used for the 10 imputations are selected from a pseudo-random number table in Steele and Torrie (1960) and are 70303, 18191, 62404, 26558, 92804, 15415, 02865, 52449, 78509, and 43896.*

With regard to imputation for the primary safety endpoint, that endpoint is obtained so close to the procedure that there will be very little missing data. If any of the test subjects are lost to follow-up prior to 30 days, that patient will be assigned an MAE for primary analysis purposes.

In addition to the above missing data analyses, Tipping Point analyses will also be performed. For each imputed data set, one MAE will be added and the exact binomial test will be done. The number of steps required to achieve non-significance of the MAE endpoint will be reported for each imputation. The supportive tipping point analysis will be repeated for the completed cases and will be done in the same way by adding one MAE and doing an exact binomial test of the result. The number of steps required to achieve non-significance will be reported for this analysis as well.

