8.6. RECOMMENDED SECONDARY INTERVENTION TREATMENT OPTIONS (ALSO KNOWN AS BAILOUT PROCEDURES)

Endologix submitted an Unanticipated Adverse Device Effect (UADE) report to the FDA on October 14, 2016 to report higher than anticipated rates of migration, endoleak (Type IA), and AAA sac enlargement, based on the 2-year follow-up data from the Nellix US IDE trial. As part of the investigation of the higher than anticipated rates of Type 1A endoleaks, migration and AAA sac enlargement, Endologix, in consultation with physicians, reviewed alternative treatment options from clinical studies, commercial use, literature, physician experience and use in similar technologies (e.g., EVAR) to develop a list of recommended treatment options. For many of the treatment options, the clinical data to support the safety and effectiveness of the treatment is limited.

The treating physician should consider multiple factors such as subject anatomy, subject risk profile, hospital standard of care and physician preference when determining the appropriate treatment option. Endologix's treatment recommendation is based on a subset of those factors, and as such, should be used as a reference for physicians and not a requirement. Each secondary intervention case requiring an additional Nellix device will undergo an internal review process. Implanting physicians in such cases will go through device training prior to their first bailout procedure and a proctor will be provided for secondary ChEVAS procedures. The recommended treatment options are provided below.

It should be noted conversion to open repair should be used if a less invasive option is not feasible for the subject, based on the physician's clinical judgment. Even with the other recommended treatment options available, conversion to open repair can be performed at any time, per the physician's discretion.

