- *Procedural Blood Loss $>1,000\text{mL}$* : Estimated blood loss during the index procedure $\geq 1,000\text{mL}$.
- *Other Definitions*:
 - *Aneurysm Sac Enlargement*: Aneurysm sac diameter increase of $>5\text{mm}$ in late follow-up as compared to the initial post-operative measurement.
 - *Aneurysm Rupture*: bleeding or leaking of blood from the aneurysm subsequent to the index procedure.
 - *Clinically significant migration*: Core Lab reported stent distal movement $>10\text{mm}$ from the original implant location relative to the center of the distal renal artery resulting in an intervention or in a serious complication.
 - *Conversion to Open Repair*: open surgical repair of the abdominal aortic aneurysm due to unsuccessful delivery or deployment of the stent graft, due to complications or other clinical situations that precluded successful endovascular treatment, or at any time following initial successful endovascular treatment for any reason.
 - *Device Positional Stability*: Core Lab reported position of each stent relative to the center of the L3 vertebrae. Stable positioning is defined as within 5mm of the positioning on the first post-operative CT scan.
 - *Luminal Thrombus Requiring Intervention*: any endovascular surgical intervention after completion of the Nellix System implantation for resolution of endograft thrombosis.
 - *Distal Ischemia*: New onset of compromised peripheral blood flow resulting in femoral or peripheral arterial occlusion or stenosis (attributable to the index procedure and not related to natural progression of atherosclerotic disease) causing a threat to the viability of the limb and requiring surgical or percutaneous intervention; or stent graft occlusion requiring any intervention..
 - *Endoleak*: Clear evidence of contrast outside of one or both EndoBags which communicates with the aneurysm sac originating proximally at the infrarenal segment (Type IA), distally (Type IB); between components, if an extender is used (Type III); trans-device (Type IV); or from a patent collateral vessel (Type II: e.g., lumbar artery; inferior mesenteric artery). Contrast outside of an EndoBag that does not communicate with the aneurysm sac is not to be reported as an endoleak.

- *Migration*: Core Lab reported stent distal movement >5mm from the original implant location relative to the center of the distal renal artery.

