10.7 PRIMARY EFFECTIVENESS ANALYSIS

10.7.1 Primary Effectiveness Hypothesis

The primary effectiveness hypothesis is that the Treatment Success rate at one year exceeds a performance goal of 80%. The hypothesis test will be evaluated using the exact binomial distribution as a one-tailed test, using significance level $\alpha=0.05$. Multivariable analyses will be used to assess predictors of success. The null and alternative hypothesis is presented below.

$$H_0: P \leq 0.80 \quad \text{vs.} \quad H_1: P > 0.80$$

Where P is the rate of Treatment Success as defined in §10.7.2.

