10.7.2 Sample Size

The primary trial effectiveness variable is the Treatment Success rate at one year post-operatively. Treatment Success is a composite of clinically-relevant outcomes, including procedural technical success and freedom from: aneurysm rupture; conversion to open repair; Type I endoleak at 12 months; Type III endoleak at 12 months; clinically significant migration; aneurysm sac enlargement; or secondary endovascular procedure up to 12 months for resolution of Type I or III endoleak, device occlusion, migration, aneurysm sac expansion and/or a device defect.

The sample size is obtained by using the exact binomial distribution using PASS 2008. A sample size of 132 subjects at one year in the study population will have 80% power against a null performance goal of 80% if the proportion of Treatment Success is 88% or higher. It is estimated that the rate of Treatment Success will be greater than 88%.

It is anticipated that the drop-out rate of the trial will be 12% or less. Because the larger of the two sample sizes after adjustment for loss to withdrawal is the one for effectiveness, a minimum

of $132/0.88 = 150$ subjects will need to be recruited for this study. Thus to allow for deviations from assumptions, 150 subjects will need to be recruited for this study.

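### LOCF for missing one-year Treatment Success has no defined carried value and, on its natural reading, leans towards success, so it is not a neutral robustness check.

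*Combined protocol and SAP*

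**What the plan says.** Section 10.7.1 tests whether "the Treatment Success rate at one year exceeds a performance goal of 80" per cent, with an exact one-sided binomial test at 0.05. Treatment Success (sections 6.2 and 10.7.2) is technical success plus the absence of a list of failures, including "Type I endoleak at 12 months; Type III endoleak at 12 months; clinically significant migration", sac enlargement, rupture, conversion and certain secondary procedures up to 12 months. Section 8.8.7 defines sac enlargement as "Aneurysm sac diameter increase of $>5\text{mm}$ in late follow-up as compared to the initial post-operative measurement".

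Section 10.2 expects about 10% of enrolled subjects to lack one-year effectiveness data. Its main imputation is a hot deck from all subjects with a one-year outcome, repeated 10 times. It then adds further sensitivity analyses: "other imputation methods; Last Observation Carried Forward (LOCF); subjects lost to follow-up considered an endpoint failure", followed by an all-success imputation and a random draw at the performance goal. The stated purpose of the sensitivity analyses is to show that the result in evaluable subjects is not biased. The plan does not say which observation LOCF carries, or how a 30-day or 6-month status becomes a one-year composite. It attaches no decision rule to the LOCF result.

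**The concern.** LOCF suits a status that is stable between the last visit and the target visit. Treatment Success is largely an absence of failures to date, and absence becomes harder to sustain with time. Sac enlargement is a change from the first post-operative scan, so it cannot be present at that scan. Endoleak is a component as read at 12 months. Migration, conversion and secondary procedures accrue. The last scheduled visit before one year is at 6 months (section 8.3). A subject lost event-free at 30 days or 6 months would be carried as a success, and any failure still to come would be erased.

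The quantity tested then becomes success as of each subject's last visit, which is more favourable than success at one year. The all-success and all-failure imputations are recognisable extremes. LOCF looks like a middle estimate, yet for early event-free losses it nearly repeats the all-success case. The other listed methods do not fill the gap. The hot deck and the random draw ignore interim status, and the tipping-point analysis in section 10.2 adds major adverse events only, so it does not examine effectiveness.

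**Working it through.** **Inputs from the documents.** Null rate 0.80 and one-sided alpha 0.05, exact binomial (10.7.1); 132 evaluable subjects, 80% power, alternative 0.88, drop-out 12% or less, 150 recruited (10.7.2); about 10% missing at one year (10.2). So m, the number missing, is 15 (10% of 150) or 18 (12%).

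**Inputs assumed.** f is the share of lost subjects' true one-year failures already visible at their last visit. The documents give no failure timing, so f runs from 0 to 1. p_m is the lost subjects' true one-year success rate: 0.80 if loss is unrelated to outcome, with 0.70 and 0.60 as illustrations of worse-than-average losses.

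**The plan's own figure.** The plan states: "A sample size of 132 subjects at one year in the study population will have 80% power against a null performance goal of 80" per cent, "if the proportion of Treatment Success is 88% or higher". With n = 132 the smallest count with P(X ≥ r | 0.80) < 0.05 is r = 114, giving size 0.038 and exact power 76.7%. The normal approximation gives 78.9%. The smallest n with exact power of at least 80% is 135. So 132 reproduces approximately, and 132/0.88 = 150 reproduces exactly. The small power shortfall is a separate matter.

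**LOCF analysis.** All 150 subjects have a value under LOCF. The pass mark is 129: P(X ≥ 129 | 150, 0.80) = 0.037, while 128 gives 0.059.

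- Chance that a lost subject is scored a success: q = 1 − (1 − p_m) × f.
- Completers' success rate, set so that the overall rate is 80%: p_c = (120 − m × p_m)/(150 − m). This is 0.80 when p_m = 0.80.
- P(pass) = Σ_k Bin(k; m, q) × P(X ≥ 129 − k | 150 − m, p_c).

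Probability of passing when the true overall rate is 80%:

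| Lost subjects' true success | m | f = 1 | f = 0.75 | f = 0.5 | f = 0.25 | f = 0 |
|---|---|---|---|---|---|---|
| 80% | 15 | 3.7% | 5.1% | 6.8% | 9.0% | 11.6% |
| 80% | 18 | 3.7% | 5.4% | 7.6% | 10.5% | 14.2% |
| 70% (assumed) | 15 | 3.7% | 5.9% | 9.1% | 13.4% | 19.1% |
| 70% (assumed) | 18 | 3.7% | 6.5% | 10.7% | 16.8% | 24.8% |
| 60% (assumed) | 15 | 3.5% | 6.8% | 11.9% | 19.3% | 29.3% |
| 60% (assumed) | 18 | 3.5% | 7.6% | 14.6% | 25.1% | 39.1% |

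**Bias in the estimate, loss unrelated to outcome.** Excess = (m/150) × 0.20 × (1 − f). At f = 0 this is 0.10 × 0.20 = 2.0 points, or 0.12 × 0.20 = 2.4 points. At f = 0.5 it is 1.0 or 1.2 points.

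**Reading the ends.** f = 0 makes q = 1, which is exactly the all-success imputation. The all-failure imputation passes with probability near zero. With loss unrelated to outcome, the pass rate reaches 10% only when f is about 0.14 or less (m = 15) or about 0.29 or less (m = 18).

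**The case against.** LOCF is one of several supportive analyses. No alpha or claim hangs on it, and it sits beside explicit best and worst cases. On the reading used here it is never more favourable than the all-success analysis, which nobody proposes to remove. Section 10.2 also allows a subgroup that is not missing at random to be assigned failure. All of this stands, and it limits the point to the interpretation of a supportive result.

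Many failures are visible before one year. Technical failure is procedural or read at the 30-day CT, rupture and conversion count when they happen, and a CT is scheduled at 6 months (section 8.4). So f = 0 is not credible as a central value, and a reader who inferred that LOCF doubles the stated alpha would be taking the unfavourable end of an unknown range. At f = 0.5 with loss unrelated to outcome, the rate is 1.4 to 1.5 times 5%.

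The bias is also not one-directional by construction. If components are carried, an endoleak seen at 6 months would score as a failure even if it were absent at 12 months. Nor is it a fault in itself that most lost subjects score as successes: at a true 80% rate most of them are successes. The fault is the excess over their true rate.

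Section 8.6 reports "higher than anticipated rates of migration, endoleak (Type IA), and AAA sac enlargement, based on the 2-year follow-up data". This shows that failures can emerge late with this device, but not how they divide between 6 and 12 months, so it is background only.

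**Conclusion.** The point holds as a weakness in one sensitivity analysis. LOCF is undefined for this composite. On its natural reading it leans mainly towards success, which does not serve the purpose section 10.2 sets for it. With loss unrelated to outcome, its chance of passing at a true 80% rate is 3.7% (f = 1), 6.8% (f = 0.5) or 11.6% (f = 0) at 10% missing, and 3.7%, 7.6% or 14.2% at 12% missing. It is higher if lost subjects do worse than average and some of their failures are still unseen. These figures rest on 150 subjects, a pass mark of 129, the no-failure-seen-yet reading, and an f that the documents do not supply.

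A reader might infer that the trial's Type I error is inflated. The documents do not support that: the primary test in section 10.7 does not use LOCF. Nor do they support the 60% or 70% success rates for lost subjects, which are illustrations only.

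**What to change.** In section 10.2 replace LOCF with:

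> A failure observed before loss is carried forward as failure. A subject lost without an observed failure has the one-year outcome imputed (10 imputations, stated seeds) from donors who were also failure-free at that subject's last attended visit. A subject lost before any post-discharge visit is imputed from all donors.

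State also whether an endoleak seen before 12 months counts as an observed failure when it has met no other component, since sections 6.2 and 10.7.2 count endoleak at 12 months.

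Keep the all-failure and all-success analyses as the bounds for outcome-related loss. The replacement does not cover that case, because it still assumes data are missing at random given interim status.

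The cost is a few sentences of plan text and a small programming change, with no new data. The sponsor loses one favourable supportive analysis.
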